### **Rationale for Primary Analysis Method**

The MMRM method has been demonstrated extensively as an appropriate choice for the primary analysis in longitudinal confirmatory clinical studies with continuous endpoints ([Mallinckrodt et al. 2008](#)). This analysis method, which is from a broader class of direct-likelihood analyses methods, makes use of fully and partially observed data sequences from individual participants by estimating the covariance between data from different time points ([Molenberghs and Kenward 2007](#)). Further, it is often useful to implement MMRM using an unstructured approach to modeling both the treatment-by-time means and the (co)variances, leading to what is essentially a multivariate normal model wherein treatment group means at the primary time point are adjusted to reflect both the actual observed data and the projected outcomes from the participants with missing data ([Cnaan et al. 1997](#); [Molenberghs et al. 2004](#); [Molenberghs and Kenward 2007](#)).

Despite careful planning and study conduct, the occurrence of missing data cannot be completely eliminated. As a direct likelihood method, the MMRM method is a preferred approach for handling missing data in such designs. MMRM is a full multivariate model in nature that avoids potential bias as a predetermined model and operates in a more general missing at random (MAR) framework ([Mallinckrodt et al. 2001](#)). Data are considered MAR if, conditional upon the independent variables in the analytic model, the missingness depends on the observed outcomes of the variable being analyzed but does not depend on the unobserved outcomes of the variable being analyzed. This assumption implies that the behavior of the post-dropout observations can be predicted from the observed variables and therefore that treatment effect can be estimated without bias with use of the observed data ([EMA 2010](#)). For studies of missing data in a controlled clinical study setting, MAR is usually considered as a plausible underlying missing mechanism ([Molenberghs and Kenward 2007](#); [Siddiqui et al. 2009](#); [Mallinckrodt et al. 2008, 2013](#)). The assumption of MAR is often reasonable because, particularly in longitudinal studies wherein the evolution of treatment effects is assessed by design over time, the observed data and the models used to analyze them can explain much of the missingness ([Little and Rubin 1987](#); [Verbeke and Molenberghs 2000](#)). This point may be especially relevant in well-controlled studies, in which extensive efforts are made to observe all outcomes and factors that influence them while participants are following protocol-defined procedures. Thus, longitudinal clinical

studies by their very design aim to reduce the amount of missing not at random (MNAR) data (missingness explained by unobserved responses), thereby increasing the plausibility of MAR (Mallinckrodt et al. 2008).

### **Sensitivity and Supportive Analysis for Primary Efficacy Endpoint**

Sensitivity and supportive analysis will be performed on the primary efficacy endpoint to quantify the possible impact of missing data and to demonstrate the robustness of the conclusions. See below for details about missing data handling, placebo-based imputation, and a tipping-point analysis.

Furthermore, the primary analysis will be repeated using a hypothetical (de jure) estimand where data collected after rescue medication is initiated will be omitted. This can be viewed as addressing a per protocol estimand, or more simply the applicable estimand if all participants completed the first 3 weeks of follow-up without any rescue or without any missing data.

Summary statistics on total sBA by treatment group and visit will also be presented. In addition, a figure with the LS mean  $\pm$ SE of change from baseline in total sBA will be presented by treatment group and visit.

In addition, a responder analysis (based on change in total sBA) may be considered. The response definition and its appropriate analysis methodology will be outlined in the SAP.

### **Missing Data**

Although the assumption of MAR, as used for the primary efficacy analysis method, is often reasonable in clinical studies, the possibility of MNAR data cannot be ruled out. Therefore, analysis valid under MNAR is desired. Both a MNAR- and MAR-based analyses will be the basis upon which sensitivity of missing data is assessed.

Sensitivity analyses to deal with missing data will use multiple imputation (MI) methods where missing values are imputed individually under both a plausible MNAR and MAR scenario. MI is a simulation-based approach where missing values are replaced using an appropriate stochastic model given the observed data and covariates, creating multiple completed datasets. These completed datasets are then analyzed using standard analysis methods (i.e., MMRM), and the different parameter estimates across the datasets are then combined to produce a unique point estimate and SE taking into account the uncertainty of the imputation process. The following 2 sensitivity analysis models, one based on the standard MAR approach and the other based on the MNAR approach, will be used to examine robustness of the primary analysis results.

Complete details of the MI procedures, including the methodology, number of imputations, and the seed of the pseudorandom number generator used to randomly generate imputations for the missing values, will be prespecified in the SAP prior to unblinding.

### **Standard MAR Imputation**

The MAR imputation model will impute missing values using a regression-based MI model (Little and Yau 1996). For participants with complete data up to a particular visit, a multiple regression model will be fit that includes the outcome at that visit as the dependent variable and observed data (e.g., outcomes at previous visits, treatment, and baseline) as independent variables. Separate models will be similarly constructed for each visit. Using these regression

models, a missing value for a participant at a particular visit will be imputed as a draw from the predictive distribution given the outcomes at previous visits (some possibly imputed), treatment group, etc. This process will be repeated a given number of times (as specified in the SAP), resulting in the same number of complete analysis datasets. The MMRM analyses will be performed separately for each of the completed analysis datasets, and the results will be combined into 1 MI inference (Little and Yau 1996; Schafer 1997). This strategy is appropriate for datasets that have a monotone missing data pattern. If the dataset does not precisely have this pattern, a monotone data augmentation method, as described in the SAP, will be used to impute the small amount of missing data that is required to make the missing data pattern monotone before applying the MI algorithm described above.

### Placebo-Based Imputation

The placebo-based imputation analysis model assumes a MNAR mechanism and is within the pattern-mixture model framework. The pattern-mixture model approach models the distribution of a response as the mixture of a distribution of the observed responses and a distribution of the missing responses. Conceptually, pattern mixture models typically assess the outcome variable separately for different groups (patterns) and then combine results across groups for final inference (Mallinckrodt et al. 2008; Ratitch and O’Kelly 2011). The pattern-mixture model approach will be applied in the SAS MI procedure by using the MNAR statement. The MNAR imputation model will specify a subset of observations to derive the imputation model, which is used for pattern imputation based on the placebo group.

The underlying assumption is that a participant on the active treatment with missing data follows the distribution of the placebo responses (i.e., the means and the intra-participant correlations based on the placebo responses will apply). This sensitivity analysis stress-tests the MAR assumption that withdrawals will tend to have efficacy similar to participants who remain in the study in their respective treatment arm. On the contrary, the placebo-based pattern imputation assumes MNAR; that after discontinuation, participants on study drug will tend to have efficacy close to participants on placebo.

The imputations for this model are based on the distribution of placebo group responses over time. That is, an imputation model for the missing observations in the volixibat treatment group is constructed not from the observed data in the active treatment group but rather from the observed data in the placebo treatment group. This model is also the imputation model that is used to impute missing observations in the placebo group.

### Tipping Point Analysis

An additional sensitivity analysis using the tipping-point approach will be conducted to assess the robustness of the primary analysis approach. If it is plausible that, for the active treatment group, the distribution of missing primary endpoint responses has a smaller expected reduction than that of the corresponding distribution of the observed primary endpoint responses, the conclusion under the MAR assumption should be examined. It is desired to impose a fixed and definite set of quantities to encapsulate the change in efficacy associated with withdrawal (missing) for the active treatment group and independently for the placebo group. The tipping point MI analysis as described by Ratitch et al. (2013) will be applied. Tipping point analysis is a means of exploring the influence of missingness on the overall conclusion from statistical

inference by positing a wide spectrum of specifications regarding the missingness mechanism (from less pessimistic to more pessimistic). The analysis finds a (tipping) point in this spectrum of specifications, at which conclusions change from being favorable to the experimental treatment to being neutral. After such a tipping point is determined, clinical judgment can be applied as to the plausibility of the specifications underlying this tipping point. The tipping point can be identified while the result is no longer statistically significant. This imputation analysis uses a specified sequence of shift parameters, which adjust the imputed values for observations in the active treatment group and independently for the placebo group.

#### **10.4.1.2. Adjustment for Multiplicity**

In order to maintain study-wide Type I error control, an hierarchical testing procedure will be used in the comparisons between volixibat and placebo on the primary and secondary efficacy endpoints in the mITT population. The hierarchical order for testing the null hypotheses is as follows: 1) mean change in total sBA between baseline and Week 3, 2) mean change in Adult ItchRO between baseline and Week 3, and 3) the proportion of participants experiencing a composite perinatal outcome.

The effect of such a procedure is that no confirmatory claims can be based on the endpoint(s) that have a rank lower than that endpoint whose null hypothesis was the first that could not be rejected. Those tests will be considered as exploratory without any formal conclusions drawn about them.

The analysis of Part 1 will be considered separate from Part 2 and no multiplicity control will be made.

#### **10.4.1.3. Secondary Efficacy Endpoints**

The secondary efficacy endpoints (see [Section 3.2](#)) are designed to evaluate the efficacy of volixibat versus placebo for the treatment of pruritus in participants with ICP as well as composite perinatal outcomes.

The secondary efficacy endpoint for pruritus is defined as the mean change from baseline to Week 3 in the weekly average worst daily itch score as measured by the Adult ItchRO. The worst daily itch score is averaged over the 7 days preceding baseline and over the 7 days preceding each week through Week 3. If >3 days of assessments are missing from a given week, then that weekly average will be set to missing. The analysis of the Adult ItchRO will use an MMRM with a comparable model to that for the primary endpoint. The primary comparison will be made regardless of adherence to randomized treatment, treatment modification, or treatment termination and irrespective of any changes in, or initiations of, allowed concomitant therapies, while assuming prohibited medications are not available and that delivery or perinatal death prior to 3 weeks does not occur.

The attributes for this estimand are the same as for the primary estimand except for the below:

- Endpoint: Change from baseline to Week 3 of the study treatment period in the weekly averaged worst daily itch score as measured by the Adult ItchRO (average of the 7 days preceding baseline and of the 7 days preceding Week 3).
- Population-level summary: Difference in the mean change in the weekly averaged worst daily itch score

The secondary efficacy endpoint for composite perinatal outcomes is defined as the proportion of participants that experience any of the 4 outcomes specified in [Section 3.2](#). The comparison of interest is the proportion of participants meeting the composite outcome. The primary comparison will be made regardless of adherence to randomized treatment, treatment modification, or treatment termination and irrespective of any changes in, or initiations of, allowed concomitant therapies, while assuming prohibited medications are not available.

The attributes for this estimand are the same as for the primary estimand except for the below:

- Treatments: The randomized treatment administered BID until day of delivery (with at least 1 dose), regardless of adherence to randomized treatment, treatment modification, or treatment termination.
- Endpoint: Experiencing one or more of perinatal death, spontaneous preterm delivery, iatrogenic preterm delivery attributed to ICP or ICP-related complications, neonatal unit admission for  $\geq 12$  hours from birth until hospital discharge for one or more of predefined indications.
- Population-level summary: Difference between treatment groups in the proportion of participants achieving the endpoint.
- Intercurrent events: Preterm delivery or perinatal death are included as part of the endpoint definition and thus handled using a composite strategy.

For this responder-type endpoint, the number and proportion of participants that are considered a “responder” will be summarized by treatment group at Week 3 and analyzed using a stratified Cochran-Mantel-Haenszel (CMH) test to calculate the p-value for the difference between treatment groups. The p-value from the CMH test will be the basis of the hypothesis testing. Furthermore, as supportive analyses, a Logistic Regression (LR) estimator approach ([Ge et al. 2011](#)), as well as a logistic regression model with baseline sBA, gestational age, and presence/absence of gestational diabetes as covariates will be run. The model assumptions of the logistic regression model are not considered a concern because a randomized study has comparable distributions of the treatment groups for covariates and factors for stratification, although they may impact the interpretation of estimated parameters for the covariates. Most importantly, a logistic regression model addresses estimands that are conditional on the covariates in the model, with these estimands sometimes being called participant-specific, and express the extent of efficacy of a treatment that a participant might expect on the basis of her covariates, although they tend to be further from the null for an effective treatment than population average estimand. A randomization-based version of logistic regression will also be considered. It is robust to model assumptions, and it has a population average estimand that is the same as the unadjusted OR for comparing 2 treatments ([Zinc and Koch 2012](#)).

An hierarchical testing procedure, as described in [Section 10.4.1.2](#), will be used in the comparisons between volixibat and placebo on the primary and secondary efficacy endpoints for Part 2 in the mITT population using the primary analysis method (as described for the primary endpoint). Sensitivity analyses for the secondary endpoints included within the hierarchical testing procedure will be detailed within the SAP.

All tests will be performed as 2-sided tests at the 0.05 level of significance.

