### 3.2. Secondary Objectives and Endpoints

The following secondary objectives and endpoints are applicable in Part 1 and Part 2.

- To assess the efficacy of volixibat on pruritus due to ICP on the basis of the following endpoint:
  - Mean change from baseline to Week 3 of the treatment period in the weekly average worst daily itch score as measured by the Adult Itch Reported Outcome (ItchRO)
- To assess the impact of volixibat on a composite perinatal outcome in participants with ICP on the basis of the following endpoints:
  - Proportion of participants experiencing one or more of the following:
    - Perinatal death, defined as in utero fetal death after randomization or known neonatal death up to 28 days after birth
    - Spontaneous preterm delivery, defined as delivery at <37 weeks' gestational age following spontaneous onset of preterm labor or preterm premature rupture of the membranes (PPROM)
    - Iatrogenic preterm delivery attributable to ICP or ICP-related complications, defined as delivery at <37 weeks' gestational age resulting from medical intervention (i.e., augmentation/induction of labor or cesarean delivery without prior spontaneous onset of preterm labor or PPROM with one or more of the following as the indication for delivery):
      - Diagnosis of ICP with or without suspected fetal compromise
      - Persistently elevated/increasing sBA
      - Worsening hepatic function
      - Intolerable maternal ICP symptoms
    - Neonatal unit admission for  $\geq 12$  hours from birth until hospital discharge for one or more of the following indications:
      - Respiratory insufficiency/failure with requirement for oxygen supplementation
      - Noninvasive or invasive respiratory support
      - Hemodynamic instability or shock requiring clinical intervention
      - Metabolic acidosis or signs of asphyxia

- Proven infection
- Hypoglycemia or feeding problems requiring intravenous (IV) fluids or tube feeding
- Meconium-stained amniotic fluid and/or its sequelae (e.g., meconium aspiration, etc.)

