### 8.2.3. Composite Adverse Perinatal Outcomes

The composite adverse perinatal outcomes will comprise the following:

- Perinatal death, defined as in utero fetal death after randomization or known neonatal death up to 28 days after birth
- Spontaneous preterm delivery, defined as delivery at <37 weeks' gestational age following spontaneous onset of preterm labor or PPRM
- Iatrogenic preterm delivery attributable to ICP or ICP-related complications, defined as delivery at <37 weeks' gestational age resulting from medical intervention (i.e., augmentation/induction of labor or cesarean delivery without prior spontaneous onset of preterm labor or PPRM with one or more of the following as the indication for delivery):
  - Diagnosis of ICP with or without suspected fetal compromise
  - Persistently elevated/increasing sBA level
  - Worsening hepatic function
  - Intolerable maternal ICP symptoms
- Neonatal unit admission for  $\geq 12$  hours from birth until hospital discharge for one or more of the following indications:
  - Respiratory insufficiency/failure with requirement for oxygen supplementation
  - Noninvasive or invasive respiratory support
  - Hemodynamic instability or shock requiring clinical intervention
  - Metabolic acidosis or signs of asphyxia
  - Proven infection
  - Hypoglycemia or feeding problems requiring IV fluids or tube feeding
  - Meconium-stained amniotic fluid and/or its sequelae (e.g., meconium aspiration, etc.)

Data on outcomes described in the SoA ([Table 1](#)) under “Perinatal outcomes assessment” shall be collected in the eCRFs.

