#### Primary Estimand for Primary Efficacy Endpoint

The primary estimand efficacy endpoint is to evaluate the superior efficacy of volixibat versus placebo for the reduction of elevated sBA concentrations in participants with ICP. The primary comparison of interest is the mean change in sBA concentration comparing baseline with Week 3. The primary comparison will be made regardless of adherence to randomized treatment, treatment modification, or treatment termination and irrespective of any changes in or initiations of allowed concomitant therapies, while assuming that prohibited medications are not available.

The corresponding primary estimand is described by the following 5 attributes:

- Treatments: The randomized treatment administered BID until delivery (with at least 1 dose), regardless of adherence to randomized treatment, treatment modification, or treatment termination
- Population: Participants with ICP who have an sBA concentration  $\geq 20$   $\mu\text{mol/L}$  and an average daily score of  $\geq 4$  on the Adult ItchRO during the screening period. Further population criteria details are provided in [Sections 5.1](#) and [5.2](#).
- Endpoint: Change in the sBA concentration comparing baseline with Week 3
- Population-level summary: Difference in the mean change in the sBA concentration
- Intercurrent events:
  - Change in or administration of any allowed concomitant medication will be handled using a treatment policy strategy.
  - Administration of any prohibited concomitant medication will be handled using a hypothetical strategy assuming that the prohibited medications are not available and hence were not taken, so as to assess the treatment effect for the randomized treatment groups on top of allowed concomitant medication.
  - Discontinuation of randomized treatment due to all of the following reasons will be handled using a treatment policy strategy:
    - Lack of efficacy
    - Safety concerns
    - Lack of compliance to study treatment
  - Delivery prior to 3 weeks of treatment will be handled using a hypothetical strategy, assuming that delivery has not occurred. Few early deliveries are expected prior to Week 3. Participants with sBA  $< 100$  are not likely to give birth prior to 39 weeks, which is at least 3 weeks after the first dose date based on

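### The confirmatory composite perinatal outcome is to be summarised at Week 3 and CMH-tested, which conflicts with a definition that runs to delivery, neonatal discharge and 28 days after birth

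*Protocol*

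**What the plan says.** Protocol 10.4.1.3 treats the composite as a responder-type endpoint whose proportion "will be summarized by treatment group at Week 3 and analyzed using a stratified Cochran-Mantel-Haenszel (CMH) test". It then makes that test decisive: "The p-value from the CMH test will be the basis of the hypothesis testing". The Synopsis (Secondary Efficacy Endpoint Analyses) and SAP 6.2 carry the same rule. Protocol 10.4.1.2 places the endpoint last in the fixed sequence, "3) the proportion of participants experiencing a composite perinatal outcome", and SAP 3.5 agrees.

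The endpoint is defined in Protocol 3.2 and 8.2.3 and SAP 1.1.2:

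- Perinatal death is fetal death in utero after randomisation, or "known neonatal death up to 28 days after birth".
- The preterm components depend on gestational age: "Spontaneous preterm delivery, defined as delivery at <37 weeks' gestational age". The ICP-related iatrogenic component uses the same 37-week limit.
- Neonatal unit admission is counted over the "hours from birth until hospital discharge for one or more of the following indications".

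None of these carries a Week 3 limit. The Schedule of Activities (Protocol Table 1) collects perinatal outcomes at delivery and follows neonatal unit stays to resolution. Neither document says how to classify a participant who is still pregnant at Week 3.

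**The concern.** Week 3 is the right time point for the first two endpoints in the hierarchy, change in sBA and change in ItchRO. It is not a natural time point for an outcome that exists only once the baby is born and followed. The SAP also keeps the two apart: for visit-based data, Table 2 in SAP 3.8.2 gives Week 3 a window of Study Days 19 to 25, and delivery is summarised as its own visit.

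A programmer who follows the sentence as written would count a woman still pregnant at Week 3 as event-free or missing, whatever happens later. Protocol 2.2.1 calls sBA a surrogate and the composite the direct assessment of perinatal outcome, so this is the only confirmatory test of perinatal benefit. Protocol 8.3.1 and 9.1.1 also keep composite events out of AE and SAE reporting because they are captured as endpoints. Events dropped from the composite test would therefore not appear in the AE tables either.

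The wording also spreads. Protocol 10.4.1.4 and SAP 6.3 analyse the binary perinatal endpoints, and the proportion with sBA below 40 µmol/L at end of treatment, in the same manner as the composite.

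**Working it through.** **The plan's own figure.** No event rate, effect or power is stated for the composite. The only Part 2 power figure is for sBA in Protocol 10.1: 100 per arm, difference 10, SD 25, two-sided 0.05. Power = Φ(10 / (25·√(2/100)) − 1.96) = Φ(2.828 − 1.96) = 0.807, against the stated 80%. It reproduces but does not bear on the composite.

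**Date arithmetic (no assumptions).** Gestational age at Week 3 is baseline plus 3 weeks. The part of the preterm window after Week 3 is max(0, 37 − (baseline + 3)) weeks. Part 2 allows baseline from 20 weeks 0 days to 36 weeks 0 days (Protocol 5.1).

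| Baseline (weeks) | At Week 3 | Preterm window after Week 3 (weeks) |
|---|---|---|
| 28 | 31 | 6 |
| 30 | 33 | 4 |
| 32 | 35 | 2 |
| 33 | 36 | 1 |
| 34 | 37 | 0 |
| 36 | 39 | 0 |

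- Preterm components: nothing is lost for baseline at or after 34 weeks 0 days. Before that, the loss grows by one week of window for each week of earlier baseline.
- Neonatal components: for any delivery after Week 3, all of them fall outside.
- 28-day death window: for a delivery x days after baseline (x up to 21), 21 − x of the 28 days fall by Week 3. At x = 14 that is 7 days inside and 21 outside. The window always closes after Week 3.
- Inherited endpoint, full-term delivery at 39 weeks or later: 36 weeks 0 days plus 21 days is 39 weeks 0 days. Even on Study Day 25 (24 days after the first dose), baseline must be at least 39 weeks 0 days − 24 days = 35 weeks 4 days. Read at Week 3, this endpoint is nearly empty.

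**Participants exposed to some preterm loss (assumed).** Take a truncated-normal baseline with median 34.4 weeks (the cited randomised study, Protocol 4.3.2.1), cut at 36 weeks, with assumed SD 1.5 to 2.5. Then 38% to 40% are randomised before 34 weeks 0 days. This is a share of participants, not of events.

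**Share of composite events with delivery after Week 3 (assumed).** Simulation inputs, none given by the plan as its own expectation: baseline normal, centred at 30 to 34.4 weeks before truncation at 36, SD 2 or 3; delivery mean 37.0 (SD 1.3), 37.5 (SD 1.2) or 38.3 weeks (SD 1.2), at least one week after baseline; neonatal admission 8%, independent of preterm delivery; deaths not modelled.

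| Baseline centre (weeks) | Events after Week 3 |
|---|---|
| 34 to 34.4 | 45% to 72% |
| 30 to 33 | 63% to 97% |

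The 45% is the lowest scenario run, not a bound. Truncating a normal centred at 34.4 with SD 2 puts the median at 34.4 + 2·Φ⁻¹(0.5·Φ(0.8)) = 34.4 − 0.54 ≈ 33.9 weeks, and later baselines would lose less.

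**What a loss would do to power (illustrative).** Assume 100 per arm, control rate 40%, risk ratio 0.5, and the same share s of events captured in both arms. With p₁ = 0.40s, p₂ = 0.20s, Δ = p₁ − p₂ and p̄ their mean, power = Φ[(Δ − 1.96·√(2p̄(1−p̄)/100)) / √((p₁(1−p₁)+p₂(1−p₂))/100)].

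| Share captured | Power |
|---|---|
| 100% | 0.88 |
| 75% | 0.72 |
| 50% | 0.51 |
| 25% | 0.27 |

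**The case against.** The best defence is that the phrase is a slip carried over from the two Week 3 endpoints and nobody would apply it. There is support for this. The definitions, and the endpoint and intercurrent-event attributes of the composite estimand, have no Week 3 limit. The hierarchy attaches Week 3 to its first two endpoints and not to the third. Grammatically, the phrase attaches to the summary, and the CMH clause has no time point of its own. All of that stands, and it makes harm conditional on a literal reading. It does not remove the defect: the phrase appears in three places across both documents, the summary and the confirmatory test share one sentence, and no passage gives a different analysis time point.

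The other objection concerns size. A reader might infer that the rule omits most of the outcome, captures only very early events, or loses nearly all late preterm births. The documents do not support this. Protocol 10.4.1.1 says "Few early deliveries are expected prior to Week 3", but Protocol 4.3.2.1 expects relatively few participants to stay on treatment beyond 3 weeks, and treatment ends at delivery. For anyone randomised at or after 34 weeks 0 days, every preterm delivery falls by Week 3. Nor does the guidance in Protocol 8.1.12, to consider birth at 39 weeks when bile acids stay below 100 µmol/L, show that almost no one will have delivered. It has a separate branch for 100 or above, and a planned date says nothing about spontaneous or ICP-indicated preterm births, which are two of the four components.

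A reader might also see a contradiction with the estimand's treatment attribute, "The randomized treatment administered BID until day of delivery (with at least 1 dose". That describes how long treatment lasts, not when the outcome is ascertained. The primary estimand has nearly the same attribute with a Week 3 endpoint.

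**Conclusion.** The point holds as a conflict between the stated analysis time and the endpoint's own definition, in a confirmatory test. Which events a literal reading drops follows from dates alone: preterm deliveries after Week 3 when baseline is before 34 weeks 0 days, all neonatal outcomes of deliveries after Week 3, and part of the 28-day death window for earlier deliveries.

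The proportion of events dropped is not established. The range of roughly 45% to 97% rests on assumed baseline timing, delivery timing and admission rate, and the power figures on an assumed event rate and effect. They show that the loss could be substantial, not what it would be. The text should be corrected before unblinding, so that the choice between two readings is not made with results in hand.

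**What to change.** 1. In the Protocol Synopsis, Protocol 10.4.1.3 and SAP 6.2, delete the Week 3 qualifier from the composite rule.
2. State that composite status is ascertained from randomisation through delivery, the neonate's hospital discharge and 28 days after birth, whatever the week of delivery, and that the CMH test uses that completed status.
3. State how participants without that follow-up are counted. Include how vital status at day 28 is confirmed, because the F2 visit is scheduled at 28 ± 3 days after delivery and can fall on day 25.
4. In Protocol 10.4.1.4 and SAP 6.3, state that binary exploratory endpoints analysed like the composite use their own time points, including end of treatment for sBA below 40 µmol/L.

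The cost is a few sentences in each document. Delivery outcomes and neonatal stays to resolution are already collected; the only possible addition is a day-28 status check where F2 falls early. The sample size rests on sBA and does not change. No corrected power for the composite can be given, because the plan states no event rate or effect for it.
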